**c. Assignment**

The assignment of participants to each of the groups was in the order in which the initial assessments were carried out.

## **Information Biases**

For the pre and post-tests and the monitoring of training, an open trial will be conducted where the researchers and coaches will know the groups assigned (POL group and THR group) to each of the participants.

## **Adherence Strategies**

To maintain participant adherence to the research, the following activities will be carried out:

- Semi-face-to-face and virtual support (via WhatsApp and email) throughout the entire research process.
- Define as a training objective, to compete in races such as the “Bimbo Race”, “Women's Race” in distances of 5K or such as the “Bogotá Half Marathon” in distances of 10K by the middle of the semester of the year 2026.
- Weekly feedback via screenshots of your workouts (summary of your training via your GPS systems) to manage all load parameters.
- Individualized and progressive training programs based on the results of the initial tests.

## **Information Gathering**

The pre and post-tests will be carried out as shown in Table 2 on different days. On the first day, the 5km test will be performed, and 72 hours later the body composition test will be carried out, considering the recovery time necessary for the body's systems to return to their normal state after maximum effort during the tests. (Chicharro, J. 2008).

Figure 4. *Evaluation schedule*

Source: Author's own work.

## Tests

### 5000 Meter Flat Test (5km)

The 5000-meter (5K) race will be used as a means of analyzing the race time variable. Rosa-Guillamón & García-Cantó (2022) state that this race consists of covering 5000 meters, or 12.5 laps, of official outdoor athletics track at the highest possible speed. This athletic event is the shortest distance among those classified as "endurance" or long-distance races, whose main characteristic is the predominance of aerobic energy metabolism, expressed through aerobic capacity and power as a function of time and intensity of the effort. The test-retest reliability of track running tests has demonstrated high consistency coefficients, with intraclass correlation coefficient (ICC) values exceeding 0.90 reported when environmental variables such as surface, weather conditions, time of day, and warm-up standardization are adequately controlled. This level of reproducibility indicates low within-subject variability and a reduced standard error of measurement, supporting its use in intervention studies and monitoring of aerobic performance. Methodologically, Hopkins (2000) establishes statistical criteria for interpreting reliability in sports science, while Atkinson and Nevill (1998) describe procedures for quantifying measurement error and ensuring consistency in physical tests applied in a sports context—foundations that support the use of the 5000-meter test as a reliable instrument in research with adults.

A review of the literature revealed no studies using the 5-kilometer test with recreational runners in Colombia, and therefore no reference values were found. Consequently, the application of this test will serve as a reference for other studies related to recreational runners.

## Protocol

The 5 km assessment will be conducted in a group setting. Participants must wear lightweight, breathable, and comfortable athletic clothing, as well as appropriate footwear, which must remain the same for both the initial and final assessments to control for potential equipment-

related biases. Participants will be instructed to maintain their usual breakfast and refrain from physical activity for 24 hours prior to the assessment. Additionally, a minimum consumption of two liters of water per day will be recommended during the week preceding the assessment to ensure optimal hydration.

The 5 km distance will be determined by a 5 km run on the Saldarriaga Park jogging track (Chía), with a certified length of 520 meters, and the San Bartolomé La Merced School athletic track, with certified lengths of 330 meters in the inner lane and 370 meters in the outer lane. The procedure will be carried out according to the guidelines established in the World Athletics International Manual (2022), guaranteeing the validity and reliability of the protocol. Running time will be recorded independently by two evaluators using Casio HS-3 stopwatches, which have a measurement accuracy of up to 1/100 of a second. These stopwatches have been used in research such as that of Cossio -Bolaños et al. (2024), where they evaluated the validity and reliability of the falls risk scale for older adults. In turn, the dependent variable of body composition will have as indicators the percentage of body fat, the percentage of lean mass and the body mass index (BMI) and its measurement instrument will be the BIA (bioelectrical impedance) Inbody H20 with a degree of error and bias inherent to bioimpedance compared to DEXA, estimated between  $\pm 3$  and 5 percentage points (Kim J. et al., 2018; Siedler et al., 2022; Pereira et al., 2019).

Both the initial test and the final test must guarantee the same characteristics mentioned above in the protocol, to have the validity and reliability of the respective data analyses.

### **Body Composition (Inbody bioimpedance scale)**

To assess participants' body composition, an Inbody H20 segmental multifrequency bioelectrical impedance analyzer, a portable device validated in various populations, will be used. This type of device estimates percentage of fat mass, muscle mass index, and total body water percentage by measuring the body's electrical resistance (Pereira et al., 2019). Although its use is practical and accessible in academic and sports settings, the scientific literature has shown that Inbody analyzers exhibit variations compared to the reference method, dual-energy X-ray absorptiometry (DEXA).

Comparative studies report that the Inbody 770 shows a high correlation with DEXA in estimating fat-free mass and appendicular skeletal mass ( $ICC = 0.965$ ), although with small differences in estimating body fat percentage (Kim HJ et al., 2022). Similarly, Kim J. et al. (2018) found prediction errors of approximately  $\pm 4.2$  percentage points in body fat percentage estimation among the Inbody 230, 720, and 770 models compared to DEXA. Likewise, Siedler et al. (2022) identified that Inbody devices tend to underestimate body fat percentage by 3.0 to 3.4 percentage points, while maintaining high reliability in repeated measurements ( $ICC \geq 0.98$ ). Finally, Pereira et al. (2019) confirmed almost perfect associations between DEXA and Inbody 270, although they noted a systematic bias based on the sex and age of the participants.

Therefore, it is acknowledged that the absolute values obtained using BIA have an approximate margin of error of  $\pm 3$  to 5 percentage points compared to DEXA. Consequently, this study prioritizes the analysis of intraindividual changes (pre- vs. post-intervention) over comparison with external normative values.

## Measurement Procedure

Participants were asked to arrive having fasted for at least 3 hours, having refrained from strenuous exercise in the previous 24 hours, and having emptied their bladder before the measurement, following the control guidelines proposed by Kim J. et al. (2018). Assessments were always performed at the same time ( $\pm 30$  minutes) to reduce diurnal variability. Subjects stood barefoot on the plantar electrodes and held the hand electrodes according to the manufacturer's instructions. Two consecutive measurements were taken, and the average of both was used for statistical analysis.

## Quality Control and Reliability

To ensure data reliability, variables that can affect BIA, such as hydration, body temperature, prior intake, and posture, were controlled. The literature supports that, under standardized conditions, Inbody analyzers achieve intraclass correlation coefficients (ICC) greater than 0.98 in repeated measurements (Kim J. et al., 2018; Siedler et al., 2022).

## Interpretation of Results

Changes in body composition, specifically muscle mass and body fat percentage, will be analyzed between the pre- and post-intervention phases. Results were interpreted considering the inherent error and bias of bioimpedance compared to DEXA, estimated at  $\pm 3$  to 5 percentage points (Kim J. et al., 2018; Siedler et al., 2022; Pereira et al., 2019). This approach leverages the portability and low cost of Inbody without compromising the study's internal validity.

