### **Sample Size Calculation**

The sample size was calculated using EPIDAT version 4.2 for independent samples, considering a 95% confidence level ( $\alpha = 0.05$ ) and 80% statistical power ( $\beta = 0.20$ ). A standard deviation of 60 seconds was used, taken from previous studies of 5 km races in a similar population (Cruz et al., 2022), and a minimum clinically relevant difference of 60 seconds in race time between the groups was established. Under these assumptions, an approximate sample size of 8 participants per group was estimated; however, to strengthen the validity of the study and anticipate possible losses during follow-up, it was decided to include 10 participants per group, for a total of 20 participants.

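### Body-composition changes are to be read against the ±3 to 5 point disagreement with DEXA, which is an error of absolute level and not of change

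*Protocol*

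**What the plan says.** Four parts of the Protocol bear on this.

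- **Interpretation of Results** names what is analysed: "Changes in body composition, specifically muscle mass and body fat percentage, will be analyzed between the pre- and post-intervention phases". The next sentence names the error to keep in mind: "Results were interpreted considering the inherent error and bias of bioimpedance compared to DEXA", put at ±3 to 5 percentage points. No other error figure appears in that section.
- **Body Composition (Inbody bioimpedance scale)** says what the figure describes: "the absolute values obtained using BIA have an approximate margin of error of" ±3 to 5 percentage points relative to DEXA. It draws a consequence from this: "this study prioritizes the analysis of intraindividual changes (pre- vs. post-intervention) over comparison with external normative values". Among the sources of the error it lists a systematic one ("Inbody devices tend to underestimate body fat percentage by 3.0 to 3.4 percentage points"), prediction errors of about ±4.2 points for body fat, and a bias that depends on sex and age.
- **Quality Control and Reliability** gives the repeatability: "Inbody analyzers achieve intraclass correlation coefficients (ICC) greater than 0.98 in repeated measurements".
- **Measurement Procedure** plans duplicates: "Two consecutive measurements were taken, and the average of both was used for statistical analysis".

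**The concern.** The two body-composition sections point in different directions. The device section treats the gap to DEXA as a limit on absolute values and, for that reason, works with change within the person. The interpretation section then takes up the same gap as the context for reading those changes. It does not mention repeatability, which is the property that governs how well a change is measured.

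What is at stake is the secondary question, a comparison of the arms on body composition in 20 runners, for which no effect size is stated. If the sentence is applied to changes as it stands, a change or arm difference of, say, 2 points could be set aside as device error even though it was measured well. Because the sentence carries no rule, it could also be invoked or ignored once the results are known.

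Two smaller points add to this. Both numerical errors that the device section reports against DEXA (±4.2, and 3.0 to 3.4) concern body fat percentage, yet the interpretation section applies the band to muscle mass as well, which the operationalization table allows in kilograms. And the models named in the device section are the 230, 270, 720 and 770, whereas the trial uses the H20.

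**Working it through.** The plan has no design figure to reproduce here: it states no power, effect size or SD for body composition, and ±3 to 5 points is a literature value. The check has two steps.

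**Step 1: what cancels.** Write a reading as true value + person-specific bias + repeat error. In final minus initial, a bias that is the same at both visits drops out, so a constant underestimation of 3.0 to 3.4 points contributes nothing to the change. A bias component that shifts over 12 weeks but is shared by both arms drops out of the arm contrast. What remains is repeat error plus any person-specific bias that drifts. The protocol does not say how much of the ±4.2 point prediction error is stable within a person.

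**Step 2: size of the repeat error.** Inputs:

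- ICC = 0.98 (Quality Control and Reliability; the text says greater than this, so 0.98 is the cautious value).
- Two readings per visit, averaged (Measurement Procedure).
- 10 per arm (Sample Size Calculation: "it was decided to include 10 participants per group, for a total of 20 participants").
- Between-person SD of body fat percentage: not in the document. Assumed 5 to 8 points, with 10 as a further check.

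Formulas:

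- SEM = SD × √(1 − 0.98)
- 95% detectable individual change, one reading per visit = 1.96 × √2 × SEM
- The same for the mean of two readings: divide by √2, if the duplicate errors are independent
- 95% half-width of the arm difference in mean change from technical error alone, mean of two readings = t(18) × SEM × √(2/10), with t(18) = 2.10; multiply by √2 for single readings

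Worked for SD = 5: SEM = 5 × 0.1414 = 0.71. Detectable change = 1.96 × 1.414 × 0.71 = 1.96 for one reading, and 1.96 / 1.414 = 1.39 for the mean of two. Arm half-width = 2.10 × 0.71 × 0.447 = 0.66.

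| Assumed SD | SEM | Detectable change, one reading | Detectable change, mean of two | Arm half-width, one reading | Arm half-width, mean of two |
|---|---|---|---|---|---|
| 5 | 0.71 | 1.96 | 1.39 | 0.94 | 0.66 |
| 6 | 0.85 | 2.35 | 1.66 | 1.13 | 0.80 |
| 7 | 0.99 | 2.74 | 1.94 | 1.32 | 0.93 |
| 8 | 1.13 | 3.14 | 2.22 | 1.50 | 1.06 |
| 10 | 1.41 | 3.92 | 2.77 | 1.88 | 1.33 |

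All figures are in percentage points of body fat. For the planned mean of two readings, both the individual and the arm-level figures lie below 3 throughout. For a single reading, the individual figure enters the 3 to 5 band at an SD of 8.

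**The case against.** The strongest reply is that the interpretation section contains only a caveat. It sets no threshold, responder definition or equivalence margin, and it nowhere says that changes below 3 to 5 points count as noise. Read together with the device section, it can be taken as a limitation on absolute accuracy, which is the role the fix would give it.

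Much of this stands. A reader might infer that real changes will be discounted and that the secondary result is therefore biased toward no difference. The document does not support that, because the rule that would produce such a bias is not there. A reader might also conclude that the band is several times too wide. For individuals it is not: the lower end of the band, 3 points, is 3 / 2.22 = 1.4 to 3 / 1.39 = 2.2 times the detectable change for the mean of two readings, and a single reading at an SD of 8 already reaches it. For the arms, the half-widths above hold technical error only, so they do not show how wide the actual confidence interval will be.

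The inputs are also soft. The SD is assumed. The ICC is a literature value, and the device section does not say which Inbody model lies behind it. Errors of consecutive readings may not be independent, and they leave out hydration and other day-to-day variation.

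What the reply does not remove is the mismatch in the text. The section that governs interpretation speaks of changes and offers only the between-method error for reading them. The restriction to absolute values stands in a different section and is not repeated there.

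**Conclusion.** The point holds as a misdirected standard of interpretation, not as a stated rule for discarding effects. The disagreement with DEXA is not the error of a change, and the protocol's own reasoning in the device section implies as much. Applied as written, the interpretation section could lead well-measured changes or arm differences below 3 to 5 points to be dismissed as device error; it does not say that they will be.

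For scale, at an assumed SD of 5 to 8 points and the protocol's ICC of 0.98, individual detectable change is about 1.4 to 2.2 points for the mean of two readings (2.0 to 3.1 for one). The contribution of technical error to the 95% half-width of the arm difference is about 0.7 to 1.1 points. These figures rest on the assumed SD, on independent duplicate errors and on the cited ICC carrying over to the H20. They come before true variation in response and day-to-day error, both of which widen the arm-level uncertainty.

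**What to change.** Rewrite the paragraph under Interpretation of Results:

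- Keep ±3 to 5 points only as a caveat on absolute values.
- Judge individual change against the technical error from this trial's own duplicate H20 readings: SD of the duplicate differences divided by √2. This is the error of one reading. For the change between two visit means of two readings each, the error SD equals the same value (√2 × error / √2), so the 95% limit is 1.96 times it. With 20 participants and two visits there are up to 40 duplicate pairs.
- Compute it separately for each measure, so that muscle mass has its own figure in its own unit.
- Label it a lower bound, because duplicates from the same visit omit day-to-day variation.
- Read the arm comparison from the between-arm difference and its confidence interval, not against the DEXA band.

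Both readings must be kept as well as their mean. The example collection matrix (Table 6) shows one initial and one final column per measure. It is only an example, and the Inbody app is also used for collection, so the protocol does not establish that single readings are lost; it should say that they are retained. The cost is one paragraph and one extra column per measure and visit, with no added measurements.

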## Information gathering

For the collection of information from the tests applied to the variables, an Excel matrix will be used and the Inbody app will be used for this task, as evidenced in Table 5 and Table 6 below.

Table 5. Information collection method

Variable	Values or unit of measurement	Verification method	Collection method
5K race time	Minutes and seconds (e.g., 25:45)	5K Test	Excel Matrix
Body composition	% body fat, % muscle mass, body mass index (BMI kg/m  )	Bioimpedance scale	Excel Matrix and Inbody APP
Muscle mass	Kilograms or percentage (%)	Bioimpedance scale	Excel Matrix and Inbody APP

Table 6 Example of the information collection matrix

Recreational corridors	Race time		Body composition						
	Name	5K starting time	Final time 5K	initial body fat percentage	final body fat percentage	% initial muscle mass	% final muscle mass	initial BMI	final BMI

### Ethical Aspects

The principles established by the World Medical Association through the Declaration of Helsinki, and Resolution 008430 of the Ministry of Health of Colombia were considered.

### Relevance and Social Value of Research

The relevance of this study lies in its contribution to strengthening a physical culture based on scientific evidence and understanding the processes that underpin modern training. The analysis of exercise intensity models offers tools applicable in both competitive and recreational contexts, as well as promoting well-being and health. By understanding how the intensity of effort can be modulated to generate efficient and sustainable physiological adaptations, it becomes possible to design safer, more personalized training strategies that are consistent with the needs of everyone.

From a social perspective, this research is a valuable resource for athletes, coaches, and researchers interested in promoting recreational athletics and conscious, sustainable physical activity. The findings allow for a more precise understanding of the parameters that characterize the performance of recreational athletes and their relationship to physical fitness and health, fostering the development of active lifestyles and overall well-being. Thus, the study transcends the sports arena and is projected as a valuable tool for health promotion, disease prevention, and human development through responsible physical activity.

### Voluntary Participation

Participation in the study was entirely voluntary. The athletes were informed beforehand about the nature of the tests, the procedures, and the research objectives. Those who chose to participate committed to rigorously adhering to each stage of the experimental protocol, including the tests and the training process, to ensure the collection of accurate, valid, and reliable individual data.

## **Privacy and Confidentiality**

The data obtained in this research will be processed in accordance with the principles of privacy and informed consent of the participants. Participants will be duly informed about the public use of their information, always ensuring confidentiality. Only researchers will have access to the files, which are stored on systems with restricted access. Furthermore, personal identification data (such as national identification number, address, and telephone number) will be deleted, and each participant will be assigned a code. No information that could compromise their privacy will be disclosed, and the data will only be used until the publication of the study results.

## **Risk Statement**

This research was classified, according to Article 11 of Resolution 008430, as a minimal-risk study, in which maximal exercise was applied to healthy volunteers. The participants in the interventions had experience in physical training programs and therefore had a level of adaptation to the planned activities. Furthermore, they were in good health, which allowed their participation in this research to be considered safe.

Through training, the athlete will be presented with the informed consent form, which explicitly details the study, their duties, their rights, the possible risks, the benefits, among other aspects that will allow them to make a conscious and pressure-free decision to participate or not in the study. The informed consent form will be signed during that same training and/or the day before the first initial assessment that the athlete underwent, which will be a requirement to participate in the research.

## **Strategies to Minimize Risks**

Strategies to minimize risks are established based on the results obtained in initial tests and standardized indirect tests (to obtain maximum heart rate), supported by scientific evidence and literature. Workloads will be individually designed and monitored through heart rate tracking, following a structured plan grounded in scientific evidence and respecting training principles and the specific population. Assessments and interventions will be conducted in safe environments, equipped with first aid supplies, and will be carried out by qualified personnel experienced in applying the protocols.

## **Personal Benefits**

Upon completion of the research, participants are expected to strengthen their understanding of the physiological, psychological, and methodological variables that influence performance and health. Using an evidence-based approach, the aim is to promote safer, more mindful, and self-care-oriented training practices. Furthermore, the goal is for athletes to understand the importance of proper training load planning and management, along with regular physical assessments, to optimize performance and prevent injuries. This educational process extends beyond the sporting arena, fostering the development of sustainable habits that integrate body, mind, and well-being, promoting responsible, balanced, and fully conscious training practices.

